Since there is no existing decisional conflict scale (DCS) for assessing decisional conflict associated with ICD implantation, we have modified a previously validated DCS used for decision-making in breast cancer screening, influenza vaccination, and coronary revascularization procedures. This tool was also developed with the assistance of our patient, provider and general public focus groups and our stakeholder advisory panel. This DCS was tested in our pilot study and performed well. The DCS will measure the effect of the video on decisional conflict and the decision for ICD placement. The overarching goals of the DCS are to assess overall decisional conflict measured through five subscales: 1) informed subscale 2) values clarity subscale, 3) support subscale, 4) uncertainty subscale and 5) effective decision subscale. Prior to the intervention and at 1-week post intervention, participants will be asked to give their decision for ICD implantation (yes, no, unsure) followed by the administration of the DCS. Respondents will be asked to reflect on their decision and respond to the DCS questions using a 5-point Likert scale. Responses to each statement are scored 0 (strongly agree) to 4 (strongly disagree). Total scores range from 0 to 100, with higher scores indicating greater decisional conflict (Appendix B). We will compare the delta change pre to post DCS scores across study arms. To determine the effect of racial concordance between video participants (physicians and patients with ICD's and their families in the video) and study participants we will compare the delta change in pre and post DCS scores, decision for ICD implantation, and ICD receipt within 90 days of the decision in racially concordant intervention compared with racially discordant intervention.

IN-DEPTH INTERVIEW GUIDE

The Round 1 in-depth Interview Guide is designed to elicit patient perspectives on the educational information they received regarding the ICD, including information that was reassuring, concerning, confusing, etc. Patients randomized to a video arm will be asked specific questions about the video component. All patients will be asked questions regarding the conversation they had with their provider. In addition, patients will be asked a series of questions to better understand factors and individuals important to their ICD decision. The guide

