We will use the DCS to measure decisional conflict. The scale measures a person's perception of the difficulty in making a decision, the extent to which they feel uncertain about treatment options, are knowledgeable about the risks and benefits of options, clear about personal values, and supported in decision making; the scale has demonstrated good reliability (Cronbach's alpha coefficients > 0.78) and predictive validity. Higher scores indicate greater decisional conflict and patients experiencing decisional conflict are more likely to change their minds, delay decisions, express regret, and fail knowledge tests. Patients will be administered the DCS *pre* intervention at the baseline enrollment visit, and post intervention, 1-week post enrollment. Respondents will be asked to reflect on their decision and respond to the DCS questions using a 5-point Likert scale. Responses to each statement are scored 0 (strongly agree) to 4 (strongly disagree). Total scores range from 0 to 100, with higher scores indicating greater decisional conflict. **Analysis Plan:** To determine differences in decisional conflict, each group's scores will be compared using independent samples t-test at two time points or Wilcoxon rank sum test if substantial departure from normality is noted. The first comparison will be within group (pre and post intervention) followed by 2) between group differences in the change scores using analysis of covariance (ANCOVA) that adjust for baseline scores. All quantitative tests will be two-sided and conducted at the 5% level of significance. Due to the secondary nature of these comparisons, there will be no adjustment for type I error. However, it is important to note that all these group comparisons are pre-specified and results of all attempted comparisons will be reported.

Sample size estimates:

In the pilot study, among black patients, the mean and standard deviation DCS scores for UC and video groups were 36.0 ± 3.2 and 33.7 ± 4.3 respectively. Based on these data and considering two-tailed equal variances t-test and 0.05 type I error, a sample size of 480 patients will have 99% power or higher for a mean DCS difference between arms of 3.0 across standard deviations of 2.5-5.0. For a mean difference between video and usual care arms equal to 1.0, SD 2.5, power remains at >99%.

ICD IMPLANTATION RATES

Compare the proportion of patients with an ICD implanted within 90 days of study enrollment in UC vs. combined video group.

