1.2 Secondary Objectives

- Whether the proportions of patients accepting ICD in concordant video group is higher relative to discordant video group.
- To evaluate whether change (i.e. pre to post intervention improvement) in patients' knowledge of SCD and ICDs in the educational video intervention group is larger compared to change in the UC group.
- To evaluate whether change in decisional conflict from baseline to one-week follow up in the educational video intervention group is different than for the UC group. This change will also be evaluated comparing the racially concordant vs. racially discordant video.
- To evaluate whether proportion of patients with an ICD implanted within 90 days of study enrollment in the educational video intervention group is higher compared to the UC group. This proportion will be also evaluated comparing the racially concordant vs. racially discordant video.
- To determine if the time (minutes) spent with the clinician is different in the intervention compared with UC arms.

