Outcome definition: We will use the DCS to measure decisional conflict. The scale measures a person's perception of the difficulty in making a decision, the extent to which they feel uncertain about treatment options, are knowledgeable about the risks and benefits of options, clear about personal values, and supported in decision making. Higher scores indicate greater decisional conflict and patients experiencing decisional conflict are more likely to change their minds, delay decisions, express regret, and fail knowledge tests. Patients will be administered the DCS **pre**-intervention at the baseline enrollment visit and **post** intervention at 7 days post enrollment. Respondents will be asked to reflect on their decision and respond to the DCS questions using a 5-point Likert scale. Responses to each statement are scored 0 (strongly agree) to 4 (strongly disagree). Total scores range from 0 to 100, with higher scores indicating greater decisional conflict.

Analysis method: **We will compare change in DCS from baseline to 7-days (post minus pre)** between the video intervention and usual care groups using independent samples t -test or Wilcoxon rank sum test if substantial departure from normality is noted. In addition to p-values, we will provide the estimate and 95% confidence intervals of the difference in DCS pre- and post-exposure for the both groups. We will also compare across treatment groups the pre- and post-exposure DCS values. The DCS change will also be compared between the racially concordant and discordant video groups.

2.3.4 Comparison of ICD implantation status at 90 days from study enrollment.

To determine the differences in implantation rates in the video intervention versus UC arms, the difference in the proportion of patients with an ICD implanted within 90 days of study enrollment between combined video intervention arm and UC arm will be compared using the Pearson chi-square test. If necessary, the Fisher Exact Test will be used. In addition to a p-value, we will provide the estimate of difference in proportions and the 95% confidence interval (CI). We will also compare ICD acceptance at 7 days and implantation status at 90 days, overall and within randomized groups. We will use the McNemar test due to correlation of the ICD acceptance and implantation status within a patient. The above analyses will be repeated for comparison of the racially concordant and discordant video groups as well.

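### Decisional conflict: the protocol specifies baseline-adjusted ANCOVA, the SAP an unadjusted test of change, and the SAP does not clearly promise a between-arm confidence interval

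*SAP*

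**What the plan says.** - **Protocol, Decisional Conflict Scale, Analysis Plan.** Group scores are to be compared by t-test or rank-sum test at two time points. Two comparisons are then listed. The first is within group, and the second is "between group differences in the change scores using analysis of covariance (ANCOVA) that adjust for baseline scores".
- **Protocol, Study Instruments.** The same comparison appears with no test or adjustment named: "We will compare the delta change pre to post DCS scores across study arms".
- **SAP 2.3.3.** Change from baseline to 7 days (post minus pre) is compared "between the video intervention and usual care groups using independent samples t -test or Wilcoxon rank sum test". No baseline covariate is mentioned. The promised estimate is "the estimate and 95% confidence intervals of the difference in DCS pre- and post-exposure for the both groups".
- **SAP 1.2.** The objective is whether "change in decisional conflict from baseline to one-week follow up in the educational video intervention group is different than for the UC group". It continues: "This change will also be evaluated comparing the racially concordant vs. racially discordant video".
- **SAP 2.3.2 (knowledge score).** Here the interval is explicitly for the difference in changes between combined video and usual care.
- **SAP 2.3.6 (patient-provider time).** The wording is group-wise, as it is for DCS.

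**The concern.** Two different analyses are written down for one between-arm contrast, and nothing in the text supplied says which governs or why the method changed. The SAP does explain its other large departure, the move to a single primary comparison (SAP 1.5). Three things follow.

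- **Precision.** An unadjusted test of change discards information in a baseline score that every patient provides before randomization. The SAP now plans on 309 analyzable patients against the protocol's 480, so precision that costs nothing is worth more.
- **Choice of test.** If either analysis could be presented as the planned one, the nominal 5% level no longer describes the procedure.
- **Reporting.** The confidence-interval sentence could be satisfied by two within-arm intervals, without the between-arm effect that the objective asks about.

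**Working it through.** **Inputs.** Two-sided 5% level (protocol, Analysis Plan). 1:1:1 allocation (protocol, sample size). 309 analyzable patients, 103 per arm, hence 206 video and 103 usual care (SAP 1.5). Planning pairs from the protocol's DCS sample size text: 1.0 point with SD 2.5, and 3.0 points with SD 2.5 to 5.0. Assumed, because the documents do not give them: pre/post correlation r from 0.3 to 0.9, equal pre and post variances, and DCS data on all 309.

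**The protocol's own figure.** It states "For a mean difference between video and usual care arms equal to 1.0, SD 2.5, power remains at >99" per cent at N = 480. A two-sample t-test with 160 vs 320 gives 98.5% (99.2% if split 240/240), so the statement is approximately reproduced. For "a mean DCS difference between arms of 3.0 across standard deviations of 2.5-5.0", power exceeds 99.9%. At the SAP's 103 vs 206, the 1.0-point, SD 2.5 case gives 91%.

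**Variance.** With single-time SD σ:

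- change score: Var = 2(1 − r)σ²
- ANCOVA residual: Var = (1 − r²)σ²
- ratio ANCOVA / change = (1 + r)/2 = 0.65, 0.75, 0.85, 0.95 at r = 0.3, 0.5, 0.7, 0.9

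Example at σ = 2.5, r = 0.3: SD of change = 2.5√1.4 = 2.96; ANCOVA residual SD = 2.5√0.91 = 2.38. The standard error multiplier for 206 vs 103 is √(1/206 + 1/103) = 0.121.

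**Power (noncentral t) and CI half-width**, 1.0 point, single-time SD 2.5, change score vs ANCOVA:

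| r | Power, 206 vs 103 | Power, 103 vs 103 | 95% CI half-width, 206 vs 103 |
|---|---|---|---|
| 0.3 | 80% vs 93% | 68% vs 85% | 0.70 vs 0.57 |
| 0.5 | 91% vs 97% | 82% vs 91% | 0.59 vs 0.51 |
| 0.7 | 99% vs >99% | 96% vs 98% | 0.46 vs 0.42 |
| 0.9 | >99% both | >99% both | 0.27 vs 0.26 |

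The 103 vs 103 column is the concordant versus discordant video comparison.

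**If the planning SD of 2.5 is instead the SD of change** (the protocol does not say), change-score power for 1.0 point is 91% (206 vs 103) and 82% (103 vs 103) at every r. ANCOVA gives 98%, 97%, 95%, 92% and 94%, 91%, 87%, 83% at r = 0.3, 0.5, 0.7, 0.9.

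**Larger differences.** At 3.0 points and single-time SD 5.0, the least favourable case is 103 vs 103 at r = 0.3: 95% vs 99%. For 206 vs 103 at r = 0.3 it is 99% vs >99%. Every other combination is higher.

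**Validity of the SAP test.** Simulation under no effect (103 vs 206, 10,000 runs per setting) gave type I error of 5.0%, 4.7% and 4.8% for the change-score t-test at r = 0.3, 0.5, 0.7. With a true difference of 1.5, both methods averaged 1.50 to 1.51.

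**Choosing between the tests after seeing results.** Under no effect the two statistics correlate at √((1 + r)/2) = 0.806, 0.866, 0.922, 0.975. The bivariate normal probability that at least one is significant at 5% is 7.8%, 7.3%, 6.8%, 6.0% at r = 0.3, 0.5, 0.7, 0.9.

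**The case against.** The case for leaving the SAP alone has real content.

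- **The protocol is not purely an ANCOVA document.** Its DCS paragraph also names a t-test, and its DCS power rests on an equal-variance t-test. That is so, but the t-test is attached to group scores at two time points, while the between-group change is given to ANCOVA. The conflict over that contrast remains.
- **The 1.0-point case flatters the argument.** No passage calls 1.0 point clinically important. The pilot difference is 36.0 − 33.7 = 2.3 points. With the larger pilot SD, 4.3, read as a single-time SD, power at r = 0.3 is 96% vs >99% (206 vs 103) and 90% vs 98% (103 vs 103), with smaller gaps at higher r. This stands: the power gain matters mainly for small differences, although the interval narrows whatever the true effect.
- **Selective reporting is already addressed.** Both documents promise to report all comparisons, and neither adjusts secondary outcomes for type I error. This weakens the false-positive argument. The 6.0% to 7.8% figures apply only if one test is chosen after the results are seen.
- **ANCOVA's advantage is not universal.** It is a large-sample result with a common slope. With 2:1 allocation and very different slopes by arm it is not guaranteed.
- **The CI sentence may be meant as between-arm.** It follows directly on the between-arm test, and a difference can be derived from two independent within-arm results. But it does not say so, and SAP 2.3.2 shows the explicit form.
- **Naming either test would cure the conflict.** It would, but only ANCOVA also recovers the precision, and it is already the protocol's stated method.

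**Conclusion.** The point holds, at moderate weight. The documents specify different between-arm analyses of DCS change and, in the text supplied, do not reconcile them. The SAP's test is unbiased under randomization and keeps its level, so this is a matter of precision and pre-specification, not of bias. Under equal pre/post variances and a common slope, the unadjusted interval is about 24%, 15%, 8% or 3% wider at r = 0.3, 0.5, 0.7 or 0.9 (the square root of 2/(1 + r), minus 1). The practical loss is largest for small differences, low correlation and the concordant versus discordant comparison. It is slight at r = 0.9 or at 3 points. The size therefore depends on an r that the documents do not give; the textual mismatch does not. The interval sentence is a separate ambiguity, and similar wording occurs for patient-provider time. This is a secondary outcome, and the primary analysis is unaffected.

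**What to change.** In SAP 2.3.3:

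1. Name ANCOVA with arm and baseline DCS as the single between-arm analysis, as in the protocol.
2. Replace the interval sentence with a commitment to report the baseline-adjusted between-arm difference and its 95% CI, for video versus usual care and for concordant versus discordant video. Within-arm changes can stay as description.
3. Keep the rank-sum test on change as a sensitivity analysis if normality clearly fails.

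Optionally, apply the same baseline adjustment to the knowledge change in SAP 2.3.2, where the two documents do not conflict.

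The cost is a few lines of SAP wording. Baseline DCS is already collected, so no new data, visits or patients are needed.
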